#### 7.3.1.1. Presence/absence of pregnancy

Input the presence/absence of pregnancy from the start date of administration until the completion of observation period.

# 7.3.2. Targeted drug use record

The following will be recorded regarding administration of this product.

- (1) Dosage form
- (2) Dose
- (3) Body weight used for calculation of adjustment of this product
- (4) Frequency of administration
- (5) Administration period

#### 7.3.3. Concomitant therapy

# 7.3.3.1. Concomitant medications for prophylaxis of invasive fungal infections, mediations listed in precautions for coadministration / contraindication for coadministration and immunosuppressants

The following information will be recorded for concomitant medications for prophylaxis of invasive fungal infections, concomitant medications for precautions for coadministration /contraindications for coadministration, and immunosuppressants from the initiation of administration of this product until the completion date of observation period.

- (1) Drug name (product name)
- (2) Daily dose
- (3) Route of administration
- (4) Administration period

#### 7.3.4. Tests

#### 7.3.4.1. Plasma voriconazole concentration

If the plasma concentration of voriconazole was measured, input the test results.

- (1) Date and time of blood collection
- (2) Date and time of administration of this product immediately before blood collection
- (3) Plasma voriconazole concentration

#### 7.3.4.2. Laboratory tests

Input the following test items and test items for adverse events.

[Observation items] White blood cell count, neutrophil count, platelet count, total bilirubin, AST, ALT, Al-P, GGT, CRP, BUN, serum creatinine

# 7.3.5. Completion (discontinuation) record

If the administration of this product is completed or discontinued, the reason will be recorded excluding the case where the administration is continued.

If an adverse event is selected for the reason, the information in detail should be recorded in the adverse event column.

[Reason for completion]

- Completion of prophylaxis
- If the objective of administration is changed from prophylaxis to treatment, completion of administration of this product for treatment.

[Reason for discontinuation]

- For the onset of invasive fungal infections
- Adverse events (other than invasive fungal infections)
- No return to hospital
- Hospital transfer
- Other

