#### 6. RESEARCH QUESTION AND OBJECTIVES

This study is intended to assess the following items, etc. for the safety and effectiveness of Vfend 200 mg for Intravenous Use, Vfend Tablets 50 mg, Vfend Tablets 200 mg, and Vfend Dry Syrup 2800 mg (hereinafter referred to as product) in daily clinical practice for prophylactic administration of this product for invasive fungal infections in children and adults and review the necessity for further special investigation and post-marketing clinical study.

- Unknown adverse reactions including those associated with long-term use
- Occurrence of adverse reactions under actual clinical settings including long-time use
- Factors considered to affect the safety and effectiveness of this product

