# 7.2.6. Observation period

The observation period shall start on the day the administration of this product begins and ends on the day the administration is completed; provided that the patients will be followed until the last day of the investigation period as long as possible if the administration period prolongs.

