# 7.3.1. Background

Input the information at the initiation of this product

- (1) ID number
- (2) Sex
- (3) Age (at the time when the administration of the targeted drug is initiated)
- (4) Height
- (5) Body weight
- (6) Hospitalization status (inpatient/outpatient)
  (7) Objective of administration (infection for which this product is prescribed)
  -Primary prophylaxis\* / secondary prophylaxis\*\* / others
- \*Primary prophylaxis: Prophylaxis of patients without history of fungal infection

- \*\*Secondary prophylaxis: Prophylaxis of patients with history of fungal infection
- (8) History of hematopoietic stem cell transplantation (before initiation of administration or immediately after initiation of this product)
- Date of hematopoietic stem cell transplantation, type of transplantation (autograft, allogeneic full transplantation/allogeneic mini-transplantation), source of transplantation (bone marrow/cord blood/peripheral stem cell)
- Occurence of GVHD (graft versus host disease)
- Disease indicated for transplantation/severity
- (9) Presence/absence and severity of hepatic function disorder, renal impairment
- (10) Disease history (medical history and complications)
- Name of disease or syndrome, as well as history or pre-existing disease
- (11) Antifungal agents administered from the date of hematopoietic stem cell transplantation to the day before the start date of administration for prophylaxis of invasive fungal infections (name of antifungal agent, route of administration, reason for discontinuation)

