8.2. Statistical Analysis

8.2.1. Overview of Patients

• Number of sites by establisher and number of patients

In patients for whom the case report form was collected, the number and proportion of sites by establisher shown below and the number and proportion of patients will be calculated.

- University hospitals
- National hospitals established by the Ministry of Health, Labour and Welfare
- Prefectural and municipal hospitals

- Public organizations
- Hospitals other than the above four established by corporations and individuals
- General practitioners/clinics

In addition, the mean, minimum, and maximum will be calculated for the number of patients per site.

• Dispositions of patients

In patients who completed the study, the number of patients included in the analysis of safety and the number of patients included in the analysis of effectiveness will be tabulated. In addition, the number of patients excluded from the analysis of safety and effectiveness and the number of patients by reason for exclusion will be tabulated.

• Listing of discontinuations and dropouts

In the safety analysis set, the number and proportion of patients who completed or discontinued treatment will be tabulated by timing (<30 days, \geq 30 to <60 days, \geq 60 to <90 days, \geq 90 to <120 days, \geq 120 to <150 days, \geq 150 to <180 days, \geq 180 days, overall). In addition, the number and proportion of patients by reason for completion and discontinuation will be tabulated. The listing of other reasons for discontinuation will be prepared.

• Listing of excluded patients

The listing of patients excluded from the analysis of safety and effectiveness and reasons for exclusion will be prepared.

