8.2.3. Safety Analysis

Adverse drug reactions and adverse events observed during the observation period (from the day of initiation of Vfend treatment to the day of completion of treatment) + follow-up period (28 days*) will be tabulated. If the duration of the observation period + follow-up period is beyond October 31, 2018, events observed by October 31, 2018 will be tabulated. All events reported in this study will be included in listings.

*: The duration of the follow-up period in this study was set at 28 days because a 30-day follow-up period was provided in a clinical study and the period of collection of adverse events using NIS AE Report Form in this study is up to 28 days after the day of completion of treatment.

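### When prophylaxis turns into treatment with the same product, both phases are pooled in the safety, exposure and long-term tables, and no planned table separates them

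*Protocol*

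**What the plan says.** Protocol 6 states the research question as safety and effectiveness "in daily clinical practice for prophylactic administration of this product for invasive fungal infections in children and adults".

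Four provisions decide what happens when the purpose changes during use:

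- **Observation.** Under Protocol 7.2.6 the observation period "ends on the day the administration is completed". It does not stop at infection or at a change of purpose.
- **Completion record.** Protocol 7.3.5 gives as one reason for completion: "If the objective of administration is changed from prophylaxis to treatment, completion of administration of this product for treatment". Among the reasons for discontinuation is "For the onset of invasive fungal infections". For patients still on the product, "the reason will be recorded excluding the case where the administration is continued".
- **Data collected.** The objective of administration is a background item, under the instruction "Input the information at the initiation of this product". The drug-use record in Protocol 7.3.2 holds form, dose, weight, frequency and period. It has no field for purpose or for the date the purpose changed. Protocol 7.3.6.1 does collect the date of infection onset, and 7.3.7 the date of each adverse event.
- **Analysis.** SAP 8.2.2 counts the treatment period from the first to the last confirmed dose. SAP 8.2.3 tabulates events "observed during the observation period (from the day of initiation of Vfend treatment to the day of completion of treatment) + follow-up period" of 28 days, cut at October 31, 2018. The <180/≥180-day factor is built on that duration. It is used for reactions (8.2.3.1, 8.2.3.5) and for infection and success rates (8.2.4.1, 8.2.4.2). In SAP 8.2.1, "the number and proportion of patients who completed or discontinued treatment will be tabulated by timing", and reasons are tabulated as well.

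**The concern.** The protocol foresees that some patients will move from prophylaxis to treatment without changing drug, and it follows them. The SAP then treats the whole course as one exposure. Results reported for prophylaxis can therefore include reactions, days and doses from the treatment of an established infection.

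The results most exposed are those that depend on duration or on whether the product was stopped:

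- the ≥180-day tables;
- mean maintenance dose and the overdose tabulation derived from it;
- the comparison, among patients with hepatic toxicity or visual events, of those who discontinued and those who did not. The decision to stop may be made differently when an infection is being treated.

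For effectiveness by duration there is a further problem. Time accrued after the outcome helps decide which stratum a failed patient is in.

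**Working it through.** **The plan's own figure.** Protocol 7.5.2 expects at least 31 hepatic toxicity cases among 200 patients at 20% incidence, with probability about 95%. The exact binomial tail P(X ≥ 31; 200, 0.20) is 0.957, so the figure reproduces. Nothing below changes it.

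**Tracing one patient.** Take infection on Day 40, with the product continued as treatment to Day 200.

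1. Observation runs to Day 200 (Protocol 7.2.6).
2. The treatment period is 200 days, so the patient is in the ≥180-day group (SAP 8.2.2), with 40 days of prophylaxis.
3. Reactions after Day 40 enter the main tables (SAP 8.2.3), and doses after Day 40 enter the mean maintenance dose.
4. If the treatment course is finished, the patient counts as completed in the timing table. An infected patient who stops the product at onset counts as discontinued.
5. In the infection and success rates by duration, this failure sits in the ≥180-day stratum. Had the product stopped at onset, the same failure would sit in the <180-day stratum. Likewise, 120 days of prophylaxis plus 60 of treatment reaches 180.

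**Share of exposure days.** Assumptions, none of them from the documents except N = 200: 60 days of prophylaxis per patient, 90 further days of treatment for each of k switched patients. Share = 90k / (200 × 60 + 90k).

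| k | Therapeutic days | All days | Share |
|---|---|---|---|
| 2 | 180 | 12,180 | 1.5% |
| 10 | 900 | 12,900 | 7.0% |
| 30 | 2,700 | 14,700 | 18.4% |

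**Overall hepatic toxicity.** Assume 20% incidence during prophylaxis (40 of 200), a fraction f of patients switched, and a risk q of a first hepatic reaction in the therapeutic phase among those still free of one. Extra patients = 200 × f × 0.8 × q.

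- f = 1%, q = 10%: 0.16 extra patients; pooled incidence 40.16/200 = 20.1%.
- f = 10%, q = 30%: 4.8 extra patients; pooled incidence 44.8/200 = 22.4%.

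The overall incidence barely moves.

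**Main effectiveness results.** Proven or probable onset counts in the infection rate, and only patients without onset count as successes (SAP 8.2.4.1, 8.2.4.2). Onset is the event in the time-to-infection analysis, and only patients without onset are censored (8.2.4.3). What the patient takes afterwards does not enter. Only the duration strata are affected.

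**The case against.** The cohort is defined by purpose at the start of administration. Following starters through all use of the product is a legitimate, openly stated choice for a post-marketing safety study. This stands, and it is a good reason to keep the all-use tables as the main ones. A reaction soon after the switch may stem from prophylactic exposure, and the 28-day follow-up would overlap the treatment phase.

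Most of the data for a split already exist: onset date, reaction date, administration period and reason code. This also stands. It makes the fix cheap, but the SAP plans no such split.

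Some stronger readings are tempting, and the documents do not support them:

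- *The completion table hides failures and understates stopping for infection.* Completion of prophylaxis and completion after a change to treatment are separate reasons, and SAP 8.2.1 tabulates reasons, so finished switches are visible. A patient who continues the product has not stopped it. Nor is every switched patient a completer: one who stops for an adverse event has a discontinuation reason, and one still on the product has none.
- *Failed patients dominate the long-term group.* No document says how many switched patients reach 180 days. Any percentage would only return the rates put in. Stopping at infection, also provided for, shortens duration.
- *The reported dose is biased.* The dosage section gives no separate regimens for prophylaxis and treatment. It allows increases for poor response, but no systematic difference is documented.
- *The headline effectiveness results are wrong.* They are not, for the reasons given in the working.

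**Conclusion.** The point holds as a gap in the analysis plan. Observation, exposure, the reaction window and the 180-day factor all run to the last dose whatever its purpose, and no planned table separates prophylaxis from later treatment with the same product.

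Its size cannot be determined from the documents, because they give no switch rate. It may be small: under the stated assumptions, from about 1.5% of exposure days with 2 switches to 18% with 30, and little effect on overall hepatic incidence. The long-term safety tables and the effectiveness rates by duration are the most exposed. Long-term use is named in the first two objectives of Protocol 6, although the second objective in SAP 2.2 omits it.

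The change is worth making because it is cheap and stops time after failure from defining long-term prophylaxis results. The study's main conclusions do not depend on it.

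**What to change.** 1. **SAP 8.2.2 and 8.2.3:** keep the all-use tables. Add a split of reactions, treatment period and mean maintenance dose into the prophylaxis phase and the phase after change to treatment.
2. **Cut date:** use the recorded date of change of objective. If there is none, use the date of infection onset, which is already collected. One added date field on the case report form is preferable, because treatment may begin without a recorded onset. If the form can no longer be changed, the onset date and the reason code should serve for most cases.
3. **Carry-over:** show reactions in the 28 days after the cut separately, and state that prophylactic exposure may have contributed to them.
4. **Long-term factor:** for the safety and effectiveness tables by <180/≥180 days, count days of product use up to the cut. A patient whose cut falls before Day 180 then cannot be in the ≥180-day group, so the two strata should be labelled descriptive and not read as an effect of duration.
5. **SAP 8.2.1:** in the completed/discontinued-by-timing table, give patients who changed to treatment with this product their own row.

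The cost is a few extra table columns, at most one extra date field, and slightly fewer patients in the ≥180-day prophylaxis group. No all-use result is lost, and no clinical rule changes.

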#### 7.3.6. Effectiveness evaluation

#### 7.3.6.1. Presence/absence of invasive fungal infections

The result of presence or absence of invasive fungal infections during the observation period will be recorded.

If the administration with this product is continued at the completion of study period, the onset of invasive fungal infections until the completion of study period will be judged.

- (1) Presence/absence of onset
- Without onset
- With onset → Proven diagnosis\* / probable diagnosis\*\* / Possible case\*\*\* and reason for judgment
- Underminable (reason for undeterminable)

The diagnostic criteria of the European Organization for Research and Treatment of Cancer/Mycoses Study Group (EORTC/MSG) will be followed.

- \*Proven diagnosis: Patients who have clinical symptoms and findings of inflammation caused by mycosis and the causative fungi are proved from the histological diagnosis of the focus of infection or mycological diagnosis from the originally sterile site, etc.
- \*\*Probable diagnosis: At least one host factor + one clinical criterion + one mycological criterion
- \*\*\*Possible case: At least one host factor + meeting one clinical criterion but no mycological criterion
- (2) Date of onset in case of onset
- (3) Name of fungal type in case of onset, sensitivity to this product

#### 7.3.7. Adverse events

Confirm the status of adverse events from the initiation of administration of this product to the completion of observation period, and record the following information. Upon discovery of an adverse event, the attending doctor should take appropriate actions, and promptly report to Pfizer Japan Inc. (hereinafter "Sponsor"), and if causal relation with this product cannot be ruled out, the doctor should follow up the event until the adverse event or its sequelae are resolved or stabilized at the level acceptable by the attending doctor and Sponsor.

Moreover, a study should be conducted on patients in whom a serious adverse reaction, or an adverse reaction not specified in the package insert occurred if it is determined necessary by Sponsor.

- (1) Presence/absence of adverse event
- (2) Name of adverse event
- (3) Date of occurrence
- (4) Action
- (5) Seriousness
- (6) Outcome
- (7) Causality

[If the adverse event is associated with abnormal change in laboratory values, i.e., laboratory tests, the following information should also be recorded.]

- (1) Laboratory parameter
- (2) Site reference value
- (3) Unit
- (4) Date of test
- (5) Results

#### 7.3.8. Major investigation items

The following items will be major investigation items in this study.

#### (1) Hepatic toxicity

For patients who developed events related to hepatic toxicity including abnormal hepatic function test values, assess the occurrence status and the differences in patient background, dose, etc. between patients who can be continuously administered this product and patients who must be discontinued administration of this product.

#### (2) Visual events

Set the presence or absence of visual events as an investigation item. Assess the occurrence status for patients who developed visual events and the differences in patient background, dose, etc. between patients who can be

continuously administered with this product and patients who must be discontinued administration of this product.

# 7.3.8.1. Confirmation of presence/absence of adverse events that correspond to major investigation items

# 7.3.8.1.1. Presence/absence of hepatic toxicity

The presence/absence of hepatic toxicity including hepatitis, jaundice, hepatic failure, coma hepatic, ALT (GPT) increased, AST (GOT) increased, and GGT increased should be recorded for target patients in this study. If aggravation or new occurrence of hepatic toxicity is observed, the information in detail should be recorded in the adverse event column.

#### 7.3.8.1.2. Presence/absence of occurrence of visual events

The presence/absence of aggravation or new occurrence of visual events including photophobia, vision blurred, and visual disturbance should be recorded for target patients in this study. If aggravation or new occurrence of visual event is observed, the information in detail should be recorded in the adverse event column.

#### 7.4. Data sources

In this study, the investigators extract the necessary information from the medical record in accordance with the protocol.

# 7.5. Study size

#### 7.5.1. Planned sample size

200 patients (100 patients each for children and adults)

#### 7.5.2. Rationale for sample size

It was considered that the following evaluations were possible if the target sample size was set to be 200 patients in total; 100 patients each for children and adults.

Safety perspectives:

In the phase 3 study of prophylactic administration of Vfend in foreign patients with HSCT (study A1501073), the incidence of adverse reactions classified into the SOC of hepatobiliary disorders was 20.2% (47/233 patients). Of those, one patient was led to discontinuation of administration of this product. In the phase 3 study of secondary prophylactic administration of Vfend in foreign patients with HSCT (study A1501038), the incidence of adverse reactions classified into the SOC of hepatobiliary disorders was 24.4% (11/45 patients). Of those, two patients were led to discontinuation of this product. Also, in the clinical study of Vfend conducted in Japanese children (from 2 years old to under 15 years old) (study A1501096), the incidence of adverse reactions related to hepatic toxicity including abnormal hepatic function test values was 19.0% (4/21 patients). Of those, two patients were led to discontinuation of this product. Based on the above, the incidence of hepatic toxicity in patients administered this product for prophylaxis of invasive fungal infections was similar between Japanese and foreign patients and it was considered that such incidence was also similar between adults and children.

In the case where the number of patients to be collected for the special investigation for prophylactic administration of Vfend for invasive fungal infections is set to be 200 patients and the incidence of hepatic toxicity is presumed to be 20%, it is estimated that at least 31 patients with hepatic toxicity will be accumulated at a probability of about 95%. With the cumulation of this sample size, it was considered possible to compare and review the proportion of patients who discontinued the administration of this product with the clinical studies.

Although the incidence of visual events varies among different studies (study A1501073: 12.0%, study A1501038: 4.4%, and study A1501096: 42.9%), if it is presumed that there is the incidence of 5% or higher, the expected value of the incidence to be observed in 200 patients will be at least 10 patients. While it is possible that there may be no patient who discontinues the administration of this product due to visual events based on the results of clinical studies, if any patient who discontinues the administration of this product is observed, how it happened will be examined.

#### Effectiveness perspectives:

The successful rate of prophylaxis at Day 100 in the phase 3 study of prophylactic administration (study A1501073) was 54.3% (121/223 patients) and the successful rate of prophylaxis at Day 180 was 48.9% (109/223 patients). Presuming that the 50% prophylactic effect can be obtained at Day 180 by referring to the above results, the 95% CI will be 40 - 60% if the target sample size is set to be 100 patients and 43-57% if the target sample size is set to be 200 patients. The prophylactic effect can be confirmed at the estimate accuracy of about  $\pm 10\%$  if 100 patients for whom this product is administered for prophylaxis of invasive fungal infections are accumulated and that of about  $\pm 7\%$  if 200 patients are accumulated.

